7.2 Exposure Time

Exposure time is defined as the period the patient is receiving romiplostim therapy. A patient will be considered to be on “maintenance” therapy when the patient receives the same dose of romiplostim for 4 subsequent weeks.

7.3 Time at Risk

Time at risk for the NCPRR is defined as from time after initial romiplostim exposure to occurrence of outcomes listed in [Section 6.2](#). For patients without these study outcomes, the time at risk will be from the index date to death, loss to follow-up, or the end of study, whichever comes first.

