The exact sample size for the NCPRR is unknown, and is projected based upon the estimated national figure of adult chronic ITP patients, as well as the anticipated percentage of adult chronic ITP patients who may be treated with romiplostim. Based upon a conservative estimate, the study will have at least 623 adult chronic ITP patients who will receive romiplostim therapy during the study period, which will equate to more than 4,000 patient-years of follow-up. The NHRS of these 3 countries may also be capable of providing records for approximately 1,860 adult chronic ITP patients who are not exposed to romiplostim, which should provide more than 12,700 patient-years of follow-up data.

Summary of Subject Eligibility Criteria

The study population is chronic ITP patients, defined as those who have been diagnosed with ITP for more than 6 months, and who continually receive ITP treatments (eg, ITP medication), and/or have had a splenectomy procedure. Any adult (≥ 18 years) chronic ITP patient who has received at least 1 dose of romiplostim therapy, and who is registered in the NHRS of Denmark, Sweden, and Norway between 01 January 2009 and 31 December 2018, will be eligible subjects for this study. Patients will be continually followed up after discontinuation of romiplostim therapy.

Patients are excluded from the cohorts of chronic ITP patients if either of the following is present:

1. Any diagnosis of another condition associated with thrombocytopenia other than chronic ITP listed in [Appendix 2](#) at any time prior to or within 6 months after the qualifying diagnosis for chronic ITP. Examples of thrombocytopenia associated with other diseases and conditions include systemic lupus erythematosus (SLE), HIV infection, hepatitis C virus infection, malignancy, lymphoproliferative disorders, and myelodysplastic syndrome.
2. Lack of a platelet count below $150 \times 10^9/L$ without obvious cause in the 6 months before or after their first ITP diagnosis code

Comparison Group

Adult chronic ITP patients who are never exposed to romiplostim during the study period will be in the comparison group known as the romiplostim Unexposed Cohort. If patients in the comparison

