3. PATIENT REGISTRY STUDY PLAN

3.1 Registry Design

The NCPRR is established on the basis of the NHRS of 3 Nordic countries: Denmark, Sweden, and Norway.

The study period will be between 01 January 2009 (starting date) and 31 December 2019 (ending date). Interim study reports will be developed for yearly submission to the Agency. Each annual report will describe include events occurring from 01 January through 31 December of the reporting period with cumulative results. All data sources will use the same cutoff date in calendar time, December 31st of the latest year for all data obtained from the NHRS databases. The patient experience (patient time) for all patients who receive at least 1 dose of romiplostim therapy will be included in the romiplostim exposure cohort after they receive romiplostim. The patient experience with ITP time before romiplostim exposure will be included in the romiplostim unexposed cohort, along with that for all adult chronic ITP patients who never receive romiplostim therapy during the study period.

Adult chronic ITP cohorts (romiplostim Exposed Cohort and Unexposed Cohort) include adult patients who are identified as having chronic ITP (incident and prevalent cases through both hospital discharge registry and outpatient clinic registry, as described by [Frederiksen and Schmidt, 1999](#)) on or after the starting date, and up to 1 year prior to the ending date. All patients will be followed-up for **at least 1 year and up to 11 years** in either of 2 cohorts: the romiplostim Exposed Cohort or Unexposed Cohort. Incident and recurrent outcomes of interest will be assessed on an annual basis.

All clinical outcomes (eg, thrombotic/thromboembolic events, hematological malignancies, and other potential outcomes of interest) will be identified by International Classification of Diseases – 10th Revision (ICD-10) codes from the NHRS databases (eg, hospital discharge registry, outpatient clinic registry, pathology registry, death registry, cancer registry, birth registry, and prescription registry) or by review of electronic medical records and/or paper medical charts. As needed, suspected and identified cases will be medically confirmed by review of electronic medical records and/or paper medical charts, laboratory testing results, BM biopsy reports, pathology data, pharmacy data, and other relevant health records. Laboratory data will be used to determine thrombocytosis and worsened thrombocytopenia after cessation of romiplostim.

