7. REGISTRY FOLLOW-UP PERIOD, EXPOSURE TIME, AND TIME AT RISK FROM EXPOSURE

7.1 Registry Follow-up Period

The follow-up period will be separated into 4 periods:

- Six months prior to receiving romiplostim therapy: This period is considered a cohort qualification and baseline establishment period. Using this period, the eligibility of subjects will be challenged and confirmed, disease conditions will be assessed, and propensity scores will be assigned for each patient. Based on the information, study cohorts will be established.

- Under treatment period: The period is defined as being from Index Date to 10 days after the last dose of romiplostim medication. During this period, all study outcomes will be assessed except for outcomes related to latency effects and post treatment effects.
- Period immediately after romiplostim treatment cessation: This period is defined as between 10 to 100 days after the last dosing. The period will be used to assess risk of worsened thrombocytopenia after treatment cessation (eg, platelet counts, bleeding, as well as rescue medication usage). As needed, this study will separate this time period into 2 sub-time periods: (3a) time period from 10 to 30 days after the last dose; and (3b) time period from 30 days to 100 days after the last dose.
- Post treatment period: This is defined as the period from 100 days after the last dosing to the end of the study. This period, as well as the aforementioned 3 periods, will be used to study long term effects of romiplostim (eg, malignancies).

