11. STUDY SIZE CONSIDERATION

A total estimate of 623 patients (4,234 patient-years) will comprise the Exposed Cohort. According to the study design, the Unexposed Cohort for adult chronic ITP patients will include 1860 patients, and will account for 12,700 patient-years of follow-up ([Figure 1](#)). This is a conservative estimation.

The study will compare chronic ITP patients who received romiplostim with those patients who do not receive romiplostim. This study will collect approximately 4,234 patient-years of romiplostim-exposed patient information during the 11 years of follow-up. Although the background incidence rate of study outcomes in chronic ITP patients is unknown, this sample size has a greater than 80% probability of detecting a difference in a range of relative risks from 2 to 4 where the background incidence ranges for 0.5% to 5%.

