17. APPENDICES

Appendix 1. Probability of Detecting Specified Relative Risk for Estimated Incidence Rates for the Study Sample Size

Estimated Background Incidence Rate (%)	Relative Risk				
	1.25	1.50	2.00	3.00	4.00
	Power (%)				
0.1	4	9	26	69	92
0.2	6	16	50	94	99
0.5	13	40	89	99	99
1.0	24	70	99	99	99
2.0	46	99	99	99	99
5.0	85	99	99	99	99

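### One time at risk, first dose to end of study, is set for every outcome and not reconciled with the treatment periods, so off-drug years can dilute acute-outcome rates and the stated power

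*Protocol*

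**What the plan says.** Protocol Section 7.3 starts time at risk at first romiplostim exposure and ends it at the outcome. For patients without the outcome, "the time at risk will be from the index date to death, loss to follow-up, or the end of study", whichever comes first. It makes no distinction among the Section 6.2 outcomes. Section 3.1 agrees: patient time "will be included in the romiplostim exposure cohort after they receive romiplostim", with no exit at cessation. The synopsis adds: "Patients will be continually followed up after discontinuation of romiplostim therapy".

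Section 7.1 divides the same follow-up by treatment status. Of the under-treatment period it says: "The period is defined as being from Index Date to 10 days after the last dose of romiplostim medication". It continues: "During this period, all study outcomes will be assessed except for outcomes related to latency effects and post treatment effects". Days 10 to 100 after the last dose serve worsened thrombocytopenia, and the time after day 100 serves long-term effects. Section 7.2 adds: "Exposure time is defined as the period the patient is receiving romiplostim therapy". No stated rate uses that quantity as its denominator.

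On size, Section 11 says: "This study will collect approximately 4,234 patient-years of romiplostim-exposed patient information during the 11 years of follow-up". It claims more than 80% probability of detection for relative risks of 2 to 4 at background incidences of 0.5% to 5%. Appendix 1 gives the cells under the title "Probability of Detecting Specified Relative Risk for Estimated Incidence Rates for the Study Sample Size".

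**The concern.** A rate needs events and person-time from the same window, and the window should suit the outcome. Under 7.3, a patient who receives one dose in 2009 and no more contributes about ten years of exposed time to every outcome. That suits a latent outcome such as AML or MDS. For an outcome whose excess risk ends with treatment, those years carry only background risk, so the exposed rate and its ratio to the unexposed rate move toward background. In a pharmacovigilance registry, that error understates harm.

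The power statement is affected in the same way. If part of the 4,234 years is off drug, applying the full relative risk to all of them assumes either that nobody stops or that the risk persists after stopping. The protocol states neither.

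**Working it through.** **Inputs.** From Sections 3.5 and 11: 623 exposed patients with 4,234 patient-years, and 1,860 unexposed patients with 12,700 patient-years. From Appendix 1: background rates of 0.1% to 5%, read as per patient-year, and relative risks (RR) of 1.25 to 4. Assumed: two-sided 5% level, in line with the two-sided 95% interval in the synopsis, since no level is stated for power.

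**1. Are the 4,234 years drug time or follow-up?** Mean time per patient is 4,234/623 = 6.80 years exposed and 12,700/1,860 = 6.83 years unexposed. The near-equality points to follow-up time. Section 3.5 applies 5% attrition but no factor for stopping drug, and the synopsis calls the figure follow-up.

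**2. Reproduce Appendix 1.** Exact conditional comparison of two Poisson rates: given the total number of events, the exposed count is binomial with probability RR × 4,234 / (RR × 4,234 + 12,700), tested against 4,234/16,934 = 0.250. At 0.5% and RR 2, expected events are 0.005 × 2 × 4,234 = 42.3 exposed and 0.005 × 12,700 = 63.5 unexposed. Power is 89.6%, against 89% stated. The method matches 29 of the 30 cells within 2 points. The exception is 2.0% with RR 1.50: 94.2% computed, 99% stated. The table therefore applies the full RR to all 4,234 years.

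**3. Allow for off-drug time.** Let f be the share of the 4,234 years on drug. The documents do not give f, so 75, 50 and 25% are assumed. Off-drug risk is set at background.

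- Ever-exposed analysis (all events over all years): apparent RR = f × RR + (1 − f). For a true RR of 2 and f = 0.5, this is 0.5 × 2 + 0.5 = 1.50.
- On-treatment analysis: RR is unchanged, and exposed years are f × 4,234.

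At 0.5% background and a true on-drug RR of 2:

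| f | Apparent RR, ever-exposed | Power, ever-exposed | On-treatment years | Power, on-treatment |
|---|---|---|---|---|
| 100% | 2.00 | 89.6% | 4,234 | 89.6% |
| 75% | 1.75 | 70.5% | about 3,176 | 82.1% |
| 50% | 1.50 | 40.4% | 2,117 | 67.9% |
| 25% | 1.25 | 13.5% | about 1,058 | 42.4% |

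The 50% and 25% ever-exposed results are Appendix 1's own 0.5% cells for RR 1.50 and 1.25 (stated 40 and 13). Keeping 80% power needs f of about 86% on ever-exposed time and about 70% on on-treatment time.

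**4. How far does the shortfall reach?** For f = 75, 50 and 25%, on-treatment power is 99.9, 99.0 and 88.2% at 0.5% and RR 3, and 98.3, 93.2 and 71.7% at 1% and RR 2. On-treatment, the loss is mainly where background is low and RR is 2. On ever-exposed time it goes further: at 0.5%, RR 3 and f = 25%, the apparent RR is 1.50 and power is 40.4%.

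**The case against.** A reader might infer that acute events are counted only on treatment while the denominator runs to end of study, so that an on-drug share of one half would halve the rate. The documents do not support that. Section 7.1 says outcomes will be assessed in the under-treatment period but never confines them to it. Section 5.2 follows patients who have had one outcome for the others until end of study, death or loss. Taken alone, 7.3 has matching events and person-time; its fault is the mixture of on-drug and off-drug time.

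A reader might also infer that the primary rate is biased downward. That depends on the nature of the outcome. Section 2.3 calls the reticulin change reversible, but it also lists progression to an irreversible fibrotic state as a potential risk. Section 5.3 says biopsies are not routine, so a case may be found long after stopping. Ever-exposed time is defensible there. Moving the primary rate wholly to on-treatment time could lose late cases, and if drug is stopped because of early signs, the censoring would be informative.

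Some mitigation exists. Bleeding or rescue use and platelet counts are reported by period (Sections 5.4 and 6.2), which partly covers thrombocytosis. The time-varying Cox model could separate on-drug from off-drug time, but it is optional and exposure after cessation is undefined. The study is declared descriptive, so no formal decision rests on the power.

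These points limit the concern. They do not reconcile 7.1 to 7.3, and they leave thrombosis and leukocytosis with anemia without a stated on-treatment rate. In a descriptive registry the rates are the main product.

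**Conclusion.** The point stands as a should-fix. The protocol fixes one ever-exposed window for all outcomes and separately defines treatment periods and exposure time without saying which governs which rate. For outcomes with risk confined to treatment, rates and ratios are diluted by an unknown amount. At 0.5% and RR 2, the claim of more than 80% power needs about 86% of exposed follow-up to be on drug, or about 70% if analysed on treatment. The protocol states no such share.

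This rests on assumed on-drug shares, off-drug risk returning to background, and a two-sided 5% exact test. It does not show that the power claim fails throughout: on-treatment power at 0.5% and RR 3 is 88% or more for every share examined. It does not apply to latent outcomes. The 2.0% and RR 1.50 cell is a separate, minor error outside the RR 2 to 4 claim.

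**What to change.** - In 7.3, state the risk window for each outcome and take events and person-time from the same window.
- For acute outcomes, report the rate from index date to last dose plus 10 days, with the 10-to-100-day and post-100-day periods of 7.1 as separate rows.
- Keep ever-exposed time for AML, MDS and PMF. For the primary marrow endpoint, report both the ever-exposed and the on-treatment rate.
- Define exposure after cessation in the time-varying Cox model.
- Relabel the 4,234 years as ever-exposed follow-up, and restate Section 11 and Appendix 1 over a range of on-treatment years. Correct the 2.0% and RR 1.50 cell to about 94.

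The cost is wording plus a split of person-time at last-dose dates, which 7.1 already requires. The price is fewer patient-years and a less favourable stated power for acute outcomes.

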8. POTENTIAL SOURCES OF BIAS IN STUDY DESIGN

There are 4 key potential sources of bias in the study design:

Disease severity: Since romiplostim is more efficacious in treating chronic ITP than currently-marketed products, patients with more severe conditions and longer durations of the disease will receive the treatment, which should be considered as a confounding factor. Such a factor may cause a bias in the evaluation of long-term safety of romiplostim. Patients with a more severe ITP condition, for example, are more likely to have clinically significant bleeding events. Without effective methods to reduce the bias effect, the study results are questionable. To address the issue, propensity scores may be used to create strata in which the patients who are exposed and unexposed are alike

in variables that may affect outcome by forming comparisons between patients at the time of introduction to romiplostim. These variables may include disease severity, duration of disease, prior medications, and other collected variables that influence outcome. However, the prescribing patterns may not be homogeneous across the population, thereby causing minimal overlap in attributes between the exposed and unexposed. Additionally, there may be unobserved (unmeasured) differences that are not represented by the collected data. This could negatively impact the utility of propensity score stratification as there would be fewer unexposed patients with similar characteristics to the exposed patients to select for comparison.

Inconsistent reading of BM biopsy results: Because BM biopsies are taken at different time periods and reviewed by different pathologists, the consistency may be questionable, and may cause some bias. To address this issue, all BM specimens for adult chronic ITP patients will be requested to be stained for reticulin and collagen. In addition, to ensure these standards, 2 pathologists will independently, and in a blinded fashion, review all BM biopsy specimens. If diagnostic conclusions from both pathologists are inconsistent, a third pathologist will re-review the biopsies again to ascertain a final diagnosis.

Case ascertainment and confirmation: Diagnosis based on ICD-10 codes may not be able to correctly determine outcomes. The sensitivity and specificity of diagnosis based on ICD-10 codes for different diseases and conditions and for different cohorts may vary, and may induce a bias. To address this issue, the study will review electronic medical charts to confirm a diagnosis beyond ICD-10, as well as laboratory data and BM biopsy as needed.

Selection bias due to missing values: The study is based on the NHRS databases. Information for some key covariates (eg, laboratory data) may be missing for some patients. It is possible to introduce a selection bias if patients with missing values are excluded from a particular analysis. The missing value issue may also occur in development of propensity score. Patients with missing values will be excluded from the propensity development model. To address this issue, statistical methods will be employed: 1) to evaluate the mechanism of the “missingness” and 2) to impute values for missing variables based on patterns of “missingness”, if necessary.

9. REMOVAL AND REPLACEMENT OF SUBJECTS

Since the NCPRR is based upon real-life clinical practice, all patients will be followed for outcomes. For this reason, there will be no specific procedures for removal and replacement of study subjects.

10. SAFETY DATA COLLECTION, RECORDING, AND REPORTING

The NCPRR is based upon the NHRS databases. Amgen will not collect data directly from patients; however, since the study will review patient medical records, it is probable that some medical records may contain statements that link adverse events to romiplostim therapy. Amgen will instruct all medical chart reviewers to report every adverse event case that is specifically documented (or stated) in medical charts to be linked to romiplostim therapy. The collection, recording, and reporting of these cases will follow Amgen SOPs.

10.1 Safety Event Definitions

10.1.1 Definition of Adverse Events

An adverse event (AE) is any untoward medical occurrence in a patient administered a pharmaceutical product(s) and which does not necessarily have to have a causal relationship with this treatment.

An AE can therefore be any unfavorable and unintended sign (including an abnormal laboratory finding, for example), symptom, or disease temporally associated with the use of a product(s), whether or not considered related to the product(s). The definition of an AE includes:

- **Worsening of a pre-existing condition**
- **Events occurring from a medication error or overdose of a product(s), whether accidental or intentional**
- **Events occurring from abuse of a product(s)**
- **Events associated with the discontinuation of the use of a product(s), (eg, appearance of new symptoms)**
- **Any lack or loss of intended effect of the product(s)**

10.1.1.1 Adverse Drug Reactions (ADRs)

AEs that are considered related to the Amgen product(s) are classified as adverse drug reactions (ADRs).

It is the Investigator's responsibility to evaluate if an event is related to an Amgen product prior to reporting the event to Amgen.

10.1.2 Definition of Serious Adverse Events

A serious adverse event (SAE) is any AE as defined above that also:

- is fatal**
- is life threatening (places the patient at immediate risk of death)**
- requires in-patient hospitalization or prolongation of existing hospitalization**
- results in persistent or significant disability/incapacity**
- is a congenital anomaly/birth defect**
- is an "other significant medical hazard" that does not meet any of the above criteria**

A hospitalization meeting the regulatory definition for "serious" is any in-patient hospital admission that includes a minimum of an overnight stay in a healthcare facility.

"Other significant medical hazards" refer to important medical events that may not be immediately life-threatening or result in death or hospitalization, but may jeopardize the patient or may require intervention to prevent one of the other outcomes listed in the definition above. Examples of such events could include allergic bronchospasm, convulsions, and blood dyscrasias, drug-induced liver injury, events that necessitate an emergency room visit, outpatient surgery, or other events that require other urgent intervention.

10.1.2.1 Serious Adverse Drug Reactions (SADRs)

SAEs that are considered related to the Amgen product(s) are classified as serious adverse drug reactions (SADRs).

It is the Investigator's responsibility to evaluate if an event is related to an Amgen product prior to reporting the event to Amgen.

10.1.3 Definition of Other Safety Findings

Other Safety Findings include:

- Medication errors, overdose, misuse, or abuse, whether accidental or intentional, involving an Amgen product, regardless of whether associated with an ADR and/or SADR
- Pregnancy and lactation exposure regardless of whether associated with an ADR and/or SADR
- Transmission of infectious agents regardless of whether associated with an ADR and/or SADR
- Reports of uses outside the terms for authorized use of the product including off label use when associated with an ADR and/or SADR

